8.2. Adverse Events of Special Interest Analyses

The definition of AEs of special interest and their MedDRA preferred term is described as [11.6.4](#). The number and percentage of subjects experiencing an AE of special interest and the total number of AEs of special interest will be summarized. Listing will also be produced

8.3. Clinical Laboratory Analyses

Laboratory evaluations including the analyses of Chemistry laboratory tests, Hematology laboratory tests, Urinalysis, and liver function tests will be based on GSK Core Data Standards. The details of the planned displays are in [Appendix 10: List of Data Displays](#).

Clinical laboratory analyses will be by treatment group (and total for GTC1, GTC2 and GTC3) and study phases (i.e., TC1, GTC1, GTC2 and GTC3, see section [11.4](#). Note that TC1 <= 84 days and Overall will not be included for these analyses).

Raw value and change from baseline for laboratory data will be summarized by treatment group (and total for GTC1, GTC2 and GTC3) for each visit.

Shifts from baseline relative to the normal range will be also summarized by treatment group (and total for GTC1, GTC2 and GTC3) for each visit.

Worst case urinalysis results relative to baseline for protein (category: NEG, TRA, 1+, 2+, 3+, 4+) and occult blood (category: NEG, TRA, 1+, 2+, 3+) urinalysis only will be summarized by treatment group (and total for GTC1, GTC2 and GTC3) for each study phases (TC1 and GTC1, GTC2 and GTC3). The categories for worst case are: No Change/Decreased, Any Increase, Increase to TRA, Increase to 1+, Increase to 2+, Increase to 3+, Increase to 4+. The categorization is determined by comparing the baseline category to the worst case post-baseline category. The determination of the worst case post-baseline takes into account both planned and unscheduled assessments. The percentages are based on the number of subjects in the treatment group with data for the test post-baseline. Subjects with missing baseline value are to be assumed to have normal/within range baseline value.

For Chemistry and Hematology data, the scatter plots between baseline and Week12/Withdrawal will be prepared by treatment group for TC1.

In order to provide detailed information regarding liver monitoring/stopping events which are classified as adverse events in case that these events occurred, following summary and listings (IDSL number to use) will be provided.

- Summary of Hepatobiliary Laboratory Abnormalities(LIVER10)
- Listing of Medical Conditions for Subjects with Liver Stopping Events (MH2)
- Listing of Substance Use for Subjects with Liver Stopping Events (SU2)

CONFIDENTIAL

204947

- Listing of Liver Monitoring/Stopping Event Reporting(LIVER5)
- Listing of Liver Stopping Event Information for RUCAM Score(LIVER6)
- Listing of Liver Biopsy Details(LIVER7)
- Listing of Liver Imaging Details(LIVER8)
- Listing of Subjects Meeting Hepatobiliary Laboratory Criteria Post-Baseline(LIVER13)

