#### Initiation of CIC

CIC should only be initiated when one of the following criteria is fulfilled:

- PVR is  $\geq 350 \text{ mL}$  at any post treatment visit, regardless of reports of associated symptoms by subjects; or
- PVR is  $\geq 200 \text{ mL}$  and  $< 350 \text{ mL}$  and the subject spontaneously reports associated symptoms (e.g., voiding difficulties and sensation of bladder fullness) that in the opinion of the investigators/subinvestigators require CIC.

The following will occur when initiating CIC:

- 1) CIC should be performed using sterile, single-use catheters.
- 2) An adverse event of urinary retention should be recorded.
- 3) A urine analysis with a urine reagent strip as well as urinalysis, urine culture and sensitivity test at the central laboratory should be performed. In addition, these tests and analyses will be performed at scheduled visits after CIC is initiated.
- 4) The subject should be seen at a follow-up visit 1 week later, when the results of PVR measurement, associated symptoms, and a urine analysis with a urine reagent strip are

reassessed while urinalysis, urine culture and sensitivity test are performed for reassessment at the central laboratory. The investigators/subinvestigators will determine whether the subject should then be followed at regularly scheduled study visits or whether additional visits should occur.

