8. SAFETY ANALYSES

The safety analyses will be based on the “Safety” population, unless otherwise specified. In detail, each Safety population will be used for each study phase as below table. In principle, summaries for TC1 will be only by treatment group, and summaries for GTC1, GTC2, GTC3 and Overall will be by treatment group and its total.

For AEs:

Study phase	Population	Summary Group
TC1	SPDB	By treatment group
GTC1	SP1	By treatment group and total
GTC2	SP2	By treatment group and total
GTC3	SP3	By treatment group and total
Overall	SP1	By treatment group and total

NOTES:

- The definition of population is described in [Analysis Populations](#).

For other than AEs:

Study phase	Population	Summary Group
TC1	SPDB	By treatment group
GTC1, GTC2, GTC3	SP1	By treatment group and total

NOTES:

- The definition of population is described in [Analysis Populations](#).

Safety data from unscheduled visit will not be included in safety analysis (but included in listing), and safety data at last visit will be treated as Study Exit in safety analyses (but treated as Withdrawal in listing).

Visit displayed in safety analyses will be summarized below table for study phases and endpoints. SPDB (for TC1) and SP1 (for GTC1, GTC2 and GTC3) will be used for these summaries. Separate displays will be provided for TC1 and for GTCs (GTC1, GTC2 and GTC3).

Endpoints	Study phase	Study visit displayed in safety analyses table
Vital Sign	TC1	Baseline, Week 2, Week 6, Week 12, Week 18, Week 24, Week 30, Week 36, Week42, Study exit
	GTC1	Study baseline, Qualification for GTC1 [1], Week 0 [1], Week 2, Week 6, Week 12, Week 18, Week 24, Week 30, Week 36, Week42, Study exit
	GTC2	Qualification for GTC2, Week 0, Week 2, Week 6, Week 12, Week 18, Week 24, Week 30, Study exit
	GTC3	Qualification for GTC3, Week 0, Week 2, Week 6, Week 12, Week 18, Study exit
Clinical laboratory (chemistry and hematology), ECG	TC1	Baseline, Week 12, Study exit
	GTC1	Study baseline, Qualification for GTC1 [1], Week 12, Study exit

CONFIDENTIAL

204947

Endpoints	Study phase	Study visit displayed in safety analyses table
	GTC2	Qualification for GTC2, Week 12, Study exit
	GTC3	Qualification for GTC3, Week 12, Study exit
Body Weight	TC1	Baseline, Study exit
	GTC1	Study baseline, Qualification for GTC1 [1], Study exit
	GTC2	Qualification for GTC2, Study exit
	GTC3	Qualification for GTC3, Study exit
PVR	TC1	Baseline, Week 2, Week 6, Week 12, Week 18, Week 24, Week 30, Week 36, Week42, Study exit

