	GTC1	Study baseline, Qualification for GTC1 [1], Week 2, Week 6, Week 12, Week 18, Week 24, Week 30, Week 36, Week42, Study exit
	GTC2	Qualification for GTC2, Week 2, Week 6, Week 12, Week 18, Week 24, Week 30, Study exit
	GTC3	Qualification for GTC3, Week 2, Week 6, Week 12, Week 18, Study exit

NOTES:

- Baseline means study baseline defined as [5.2](#).
- Study baseline will be used for the derivation of change from baseline
- Urinalysis results will be displayed by using worst case results post-baseline relative to baseline for protein and occult blood urinalysis only in accordance with IDSL standards rationale, not by visit
- Study exit includes withdrawal.
- [1]: only for subjects with Placebo at TC 1

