11.4.1.2. Study Phases for AE Data and Safety Date except for AE

Treatment State	Definition
Pre-Treatment	AE Start Date $<$ 1st treatment Date
On-Treatment	If AE onset date is on or after treatment start date & on or before treatment stop date. 1st treatment Date \leq AE Start Date \leq Study Treatment Stop Date
Onset Time Since 1st Dose (Days)	If 1st treatment Date $>$ AE Onset Date = AE Onset Date - 1st treatment Date If 1st treatment Date \leq AE Onset Date = AE Onset Date - 1st treatment Date +1 Missing otherwise.
Duration (Days)	AE Resolution Date - AE Onset Date + 1
Treatment Cycle 1 (TC1) \leq 84 days from 1st treatment	1st treatment Date \leq AE Start Date \leq 1st treatment Date +83
Treatment Cycle 1 (TC1)	1st treatment Date \leq AE Start Date (if the subject completes / withdraws without 2nd treatment) \leq Study Exit/Withdraw Date

CONFIDENTIAL

204947

Treatment State	Definition
	or (if the subject take 2nd treatment) < 2nd treatment Date
GSK1358820 Treatment Cycle 1 (GTC1)	For subjects who received GSK1358820 as 1st treatment: 1st treatment Date ≤ AE Start Date (if the subject completes / withdraws without 2nd treatment) ≤ Study Exit/Withdraw Date or (if the subject take 2nd treatment) < 2nd treatment Date For subjects who received placebo as 1st treatment: 2nd treatment Date /Time ≤ AE Start Date / Time (if the subject completes / withdraws without 3rd treatment) ≤ Study Exit/Withdraw Date or (if the subject take 3rd treatment) < 3rd treatment Date
GSK1358820 Treatment Cycle 2 (GTC2)	For subjects who received GSK1358820 as 1st treatment: 2nd treatment Date /Time ≤ AE Start Date / Time (if the subject completes / withdraws without 3rd treatment) ≤ Study Exit/Withdraw Date or (if the subject take 3rd treatment) < 3rd treatment Date For subjects who received placebo as 1st treatment: 3rd treatment Date / Time ≤ AE Start Date / Time ≤ Study Exit/Withdraw Date
GSK1358820 Treatment Cycle 3 (GTC3)	For subjects who received GSK1358820 as 1st treatment: 3rd treatment Date / Time ≤ AE Start Date / Time ≤ Study Exit/Withdraw Date For subjects who received placebo as 1st treatment: Not applicable because 3 rd treatment of GSK1358820 is not allowed for subjects who received placebo as 1st treatment
Overall	For subjects who received GSK1358820 as 1st treatment 1st treatment Date ≤ AE Start Date ≤ Study Exit/Withdraw Date For subjects who received placebo as 1st treatment 2nd treatment Date ≤ AE Start Date ≤ Study Exit/Withdraw Date

NOTES:

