- If the study withdraw date is missing then the AE will be considered to be On-Treatment.
- AE start time needs to be considered if AE start date is equal to the re-treatment date
- As for safety date except for AE (i.e., laboratory data etc.), "AE Start Date" will be replaced with the date of measurement, unless otherwise specified.

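### Worst-case urinalysis is taken over cycles of unequal length, so arms can differ at equal per-sample risk; the tables need an equal-look row

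*SAP*

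**What the plan says.** SAP 8.3 compares each subject's baseline protein and occult blood category with the worst later category, separately for TC1, GTC1, GTC2 and GTC3. Tables 3.113 (TC1, by arm) and 3.114 (GTCs) carry the result. The worst case draws on every sample: "The determination of the worst case post-baseline takes into account both planned and unscheduled assessments". The denominator ignores how many samples a subject gave: "The percentages are based on the number of subjects in the treatment group with data for the test post-baseline".

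No other urinalysis summary is planned. The notes to SAP 8 say "Urinalysis results will be displayed by using worst case results post-baseline relative to baseline for protein and occult blood urinalysis only", not by visit. Adverse events also have a TC1 summary limited to the first 84 days, but 8.3 withholds that window from laboratory data: "Note that TC1 <= 84 days and Overall will not be included for these analyses".

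Cycle length depends on re-treatment. In SAP 11.4.1.2 the TC1 row for a re-treated subject reads "if the subject take 2nd treatment) < 2nd treatment Date". For other subjects TC1 runs to study exit or withdrawal. For laboratory data, the event date in that table "will be replaced with the date of measurement, unless otherwise specified".

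On unscheduled data the SAP disagrees with itself. SAP 8 states "Safety data from unscheduled visit will not be included in safety analysis (but included in listing", and SAP 11.5.2 likewise keeps unscheduled visits out of summary tables. Both SAP versions contain the conflict.

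**The concern.** The chance that at least one sample shows an increase grows with the number of samples, and here that number depends on outcome. Under Protocol 5.3, re-treatment requires the patient's request and at least two urgency incontinence episodes in the diary. The SAP tests time to request and time to qualification between arms as measures of treatment effect. If the drug works, placebo subjects should leave TC1 earlier and be sampled less often.

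Raised post-void residual volume (PVR) and the use of catheterisation (CIC) add unscheduled samples. At the start of CIC, for example, the protocol says "A urine analysis with a urine reagent strip as well as urinalysis, urine culture and sensitivity test at the central laboratory should be performed".

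At stake is how a safety table is read. A higher percentage on active could reflect longer observation and not the drug, and the table gives no means of telling the two apart. The conflict over unscheduled samples also means that a programmer cannot follow both rules.

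**Working it through.** The documents state no figure for worst-case urinalysis, so there is none to reproduce.

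**Samples per subject.** Visits fall at Weeks 2, 6 and 12 and then every 6 weeks to Week 48 (Protocol 4.1). Central urinalysis is done at all study visits (Protocol 7.4.6.2.1), and the panel includes protein and occult blood (Protocol Table 3). Scheduled TC1 samples are 3 if re-treated at Week 12, 4 at Week 18, 5 at Week 24, 7 at Week 36 and 9 if never re-treated. Protocol Table 2 also schedules urinalysis at the qualification visit and before dosing on the re-treatment day. It is unclear whether these count in the earlier cycle. The TC1 row uses dates only, while a note to SAP 11.4.1.2 says time matters on a re-treatment date. The Week 12 figure is therefore about 3 to 5.

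**Formula.** Assume the same per-sample chance p in both arms and independent samples. The chance of at least one increase in k samples is f(k) = 1 − (1 − p)^k. If a fraction r of an arm is re-treated at Week 12 and the rest never, the arm percentage is r·f(3) + (1 − r)·f(9). The gap, active minus placebo, is (r_placebo − r_active) × [f(9) − f(3)].

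**Final analysis, assuming r = 70% on placebo and 40% on active.** Mean samples are 0.7×3 + 0.3×9 = 4.8 on placebo and 0.4×3 + 0.6×9 = 6.6 on active.

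| p | f(3) | f(9) | Placebo | Active | Gap (points) |
|---|---|---|---|---|---|
| 2% | 5.9% | 16.6% | 9.1% | 12.3% | 3.2 |
| 5% | 14.3% | 37.0% | 21.1% | 27.9% | 6.8 |
| 10% | 27.1% | 61.3% | 37.3% | 47.6% | 10.2 |

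Gaps are computed before rounding. At p = 5%:
- With 4 or 5 samples in place of 3 for re-treated subjects, the gap is 0.3 × (37.0 − 18.5) = 5.5 or 0.3 × (37.0 − 22.6) = 4.3 points.
- With 60% against 40% re-treated and 3 samples, it is 4.5 points.
- With equal re-treatment it is 0.

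**24-week interim.** Table 3.113 is also produced here, where a subject not re-treated has 5 scheduled samples. The 70%/40% gap is 0.3 × [f(5) − f(3)] = 0.3 × (22.6 − 14.3) = 2.5 points at p = 5%, and 0.3 × (41.0 − 27.1) = 4.2 at p = 10%.

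**Unscheduled samples.** Protocol 4.6.1 gives urinary retention of 7.1% on active and 0.5% on placebo in earlier studies. With 2 or 3 extra samples per case, the added gap is (0.071 − 0.005) × [f(k+2 or k+3) − f(k)]. For k = 3 or 9 and p from 2% to 10%, this is 0.2 to 1.3 points. The rate of PVR of 200 mL or more without CIC is not given, so the contribution could be larger.

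**Cycles.** The maximum numbers of scheduled samples are 9 in GTC1, 7 in GTC2 and 5 in GTC3, but these are ceilings. An active-first subject injected at Weeks 0, 12 and 24 has 3, 3 and 5. One injected at Weeks 0 and 36 has 7 and then 3.

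**Equal looks.** Restricted to Weeks 2, 6 and 12, every fully observed cycle has k = 3. At equal risk the expected percentages then agree: 14.3% in both arms at p = 5%.

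**The case against.** The case for leaving the table alone has four parts.

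- **Assumptions.** Every arm-level figure rests on assumed re-treatment rates, per-sample risk and independence. This stands, and it limits what can be said about size. Positive correlation between one person's samples shrinks the gap, and equal re-treatment removes the part due to scheduled samples.
- **The interim.** The regulatory-submission analysis is cut at 24 weeks, where the scheduled counts are much closer. This also stands, but the final table remains exposed.
- **Other displays.** A clinically significant urinalysis abnormality is an adverse event (Protocol 12.3.1), so it enters the 84-day event tables. Follow-up duration is in Tables 1.17 and 1.18, and subjects with any out-of-range laboratory value are in Listing 30. These give context but do not correct the percentages.
- **Purpose.** Worst case is the sponsor's standard urinalysis display and is meant to miss nothing. Samples after raised PVR or CIC may carry real treatment effects. This is a good reason to keep the all-sample result, and no reason to omit a comparable one.

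A reader might infer that falling sample counts bias GTC1 to GTC3 towards apparent improvement with repeated dosing. The documents do not support that. The counts 9, 7 and 5 are maxima, a third injection by Week 36 requires short earlier cycles, and GTC3 contains active-first subjects only. A reader might also give unscheduled PVR and CIC samples equal weight with re-treatment timing. At the documented retention rates they contribute little.

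**Conclusion.** The point holds in a limited form. The planned worst-case tables compare arms and cycles over unequal numbers of samples, with no equal-look alternative for urinalysis. If placebo subjects are re-treated sooner, the final TC1 table can show more increases on active with no difference in per-sample risk. A gap of about 7 points (21% against 28%) is an illustration conditional on the 70%/40% split, all at Week 12, 5% per sample and independence. It is not a prediction.

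It would go too far to say that the table is certain to show spurious harm on active, because the documents give neither re-treatment rates nor per-sample risk. Comparisons between GTCs are not like for like, but their direction is not established. The table is descriptive, with no test planned, so no efficacy conclusion or error rate is affected. The conflict between SAP 8.3 and SAP 8 and 11.5.2 needs resolving whatever the size of the effect.

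**What to change.** In SAP 8.3 and Tables 3.113/3.114:

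1. Add a worst-case row limited to the scheduled Week 2, 6 and 12 samples of each cycle, and name it as the comparison to read between arms and cycles. Use nominal visits and not the 84-day window. The Week 12 target is Day 85, so that window would drop samples taken on schedule. Nominal visits also keep separate qualification and pre-dose samples out of this row.
2. Apply the existing SAP 11.3.2 mapping, so that a Week 48 sample can serve as Week 12 of a cycle opened at Week 36.
3. Keep the all-sample worst case, planned and unscheduled, as a separate row labelled as unadjusted for the number of samples.
4. State in 8.3 that the all-sample row is an explicit exception to the exclusion of unscheduled visits in SAP 8 and 11.5.2.

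The cost is a few sentences, a visit filter and one extra row block per table. The comparative row uses fewer samples, so findings after Week 12 or at unscheduled visits appear only in the all-sample row and the listing.

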8.4. Other Safety Analyses

The analyses of non-laboratory safety test results including ECGs and vital signs will be based on GSK Core Data Standards, unless otherwise specified. The details of the planned displays are presented in [Appendix 10: List of Data Displays](#).

ECG findings (Normal, Abnormal - not clinically significant, Abnormal – clinically significant) will be summarized by treatment group (and total for GTC1, GTC2 and GTC3) for each visit.

Raw value and change from baseline for vital sign data will be summarized by treatment group (and total for GTC1, GTC2 and GTC3) for each visit.

Any other safety endpoint will not be described in this RAP.

8.5. Study Specific Safety Analyses

Since urinary events are of interest for this study, some study specific safety analyses will be analysed for following item.

SPDB (for TC1) and SP1 (for GTC1, GTC2 and GTC3) will be used for these summaries.

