## **9.3. Data Analysis Considerations**

### **9.3.1. Analysis Populations**

In this study, the subjects are permitted to receive re-treatment up to 2 times. When analyzing the 2nd treatment cycle, the population will consist of the subjects who had a 1st and 2nd treatment. When analyzing the 3rd treatment cycle, the population will consist of the subjects who had a 1st, 2nd and 3rd treatment.

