Safety 1 (SP1)	
 • Comprise all subjects who receive at least one dose of GSK1358820. 	
 • Safety for at least one dose of GSK1358820 treatment

CONFIDENTIAL

204947

Population	Definition / Criteria	Analyses Evaluated
Safety 2 (SP2)	
 • Comprise all subjects who receive at least two doses of GSK1358820. 	
 • Safety for two doses of GSK1358820 treatment
Safety 3 (SP3)	
 • Comprise all subjects who receive three doses of GSK1358820. 	
 • Safety for three doses of GSK1358820 treatment

NOTES :

- Please refer to [Appendix 10: List of Data Displays](#): List of Data Displays which details the population to be used for each displays being generated.

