8.5.2. Clean Intermittent Catheterization (CIC)

Proportion of subjects who had used CIC at least once after the first treatment will be summarized by treatment group (and total for GTC1, GTC2, GTC3 and Overall) and study phases (TC1, GTC1, GTC2 and GTC3). As described in 8.5.1, only data of use of CIC with the reason for urinary retention or elevated PVR will be used for any analyses.

Proportion of subjects initiating CIC by raw PVR urine volume category of maximum PVR volume in TC1 will be summarized by treatment group. This summary is only for TC1. The category is described in 8.5.1.

[figure not shown]
Duration of using CIC will be summarized by treatment group (and total for GTC1, GTC2, GTC3 and Overall) and study phases (TC1, GTC1, GTC2 and GTC3) and listed. This listing includes the CIC with the reason for urinary retention or elevated PVR not include CIC with reason for “other”. Duration of using CIC is calculated cumulatively as

(Duration of using CIC in a given TC) = Sum of {(Date of A) – (later of “start date of CIC” or “date of the study drug treatment in this TC if not initiating CIC at this TC”) + 1}

- (For CIC not using at date of study complete or withdrawal) *Date of A = (earlier of “stop date of CIC” or “the day before the day of the study drug treatment for next TC if using CIC at re-treatment”)*
- (For CIC using at date of study complete or withdrawal) *Date of A = (later of “stop date of CIC” or “date of study complete or withdrawal”)*

In this calculation, if a given subject use CIC across next study drug treatment, the day of study drug treatment will be regarded as the use of CIC in next TC.

Below figure is to illustrate the example of duration of using CIC calculation.

In this example, this subject had CIC five times. In the calculation of each duration of using CIC in TC1,

- Duration of CIC 1st; day 9 – day 3 + 1 = 7
- Duration of CIC 2nd; day 22 – day 20 + 1 = 3
- Duration of CIC 3rd in TC1; (day 85 -1) – day 80 + 1 = 5

As result, duration of using CIC in TC1 is 7 + 3 + 5 = 15 days.

CONFIDENTIAL

204947

In the calculation of each duration of using CIC in TC2,

- Duration of CIC 3rd in TC2; day 91 – day 85 +1 = 7
- Duration of CIC 4th; day 203 -day 201 +1 = 3
- Duration of CIC 5th; day 225 – day 211 + 1 = 15

As result, duration of using CIC in TC2 is $7 + 3 + 15 = 25$ days.

Time to onset of first CIC will be summarized in TC1 analysed according to “Study Specific Safety Analyses for Time to Event data” below table.

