3.66.	SPDB	AE1	Summary of Special Interest Adverse Events: TC1 <= 84 days from the first treatment		Y	
3.67.	SPDB	AE1	Summary of Fatal Serious Adverse Events: TC1	GSK CTR	Y	Y
3.68.	SPDB	AE1	Summary of Serious Adverse Events: TC1	IDSL / GSK CTR	Y	Y
3.69.	SPDB	AE3	Summary of Adverse Events Leading to Withdrawal from Study / Permanent Discontinuation of Study Treatment by Overall Frequency: TC1	IDSL	Y	Y
3.70.	SPDB	AE1	Summary of Special Interest Adverse Events: TC1		Y	Y

CONFIDENTIAL

204947

Safety : Tables						
No.	Population	IDSL / TST ID / Example Shell	Title	Programming Notes	Report at Interim	Report at Final
3.71.	SPDB	AE16	Summary of Serious Adverse Events by System Organ Class and Preferred Term (Number of Participants and Occurrences) TC1	FDAAA, EudraCT	Y	Y
3.72.	SP1	AE1	Summary of Fatal Serious Adverse Events: GTC1	GSK CTR		Y
3.73.	SP1	AE1	Summary of Serious Adverse Events: GTC1	IDSL / GSK CTR		Y
3.74.	SP1	AE3	Summary of Adverse Events Leading to Withdrawal from Study / Permanent Discontinuation of Study Treatment by Overall Frequency: GTC1	IDSL		Y
3.75.	SP1	AE1	Summary of Special Interest Adverse Events: GTC1			Y
3.76.	SP1	AE16	Summary of Serious Adverse Events by System Organ Class and Preferred Term (Number of Participants and Occurrences): GTC1	FDAAA, EudraCT		Y
3.77.	SP2	AE1	Summary of Fatal Serious Adverse Events: GTC2	GSK CTR		Y
3.78.	SP2	AE1	Summary of Serious Adverse Events: GTC2	IDSL / GSK CTR		Y
3.79.	SP2	AE3	Summary of Adverse Events Leading to Withdrawal from Study / Permanent Discontinuation of Study Treatment by Overall Frequency: GTC2	IDSL		Y
3.80.	SP2	AE1	Summary of Special Interest Adverse Events: GTC2			Y
3.81.	SP2	AE16	Summary of Serious Adverse Events by System Organ Class and Preferred Term (Number of Participants and Occurrences): GTC2	FDAAA, EudraCT		Y
3.82.	SP3	AE1	Summary of Fatal Serious Adverse Events: GTC3	GSK CTR		Y
3.83.	SP3	AE1	Summary of Serious Adverse Events: GTC3	IDSL / GSK CTR		Y

CONFIDENTIAL

204947

Safety : Tables						
No.	Population	IDSL / TST ID / Example Shell	Title	Programming Notes	Report at Interim	Report at Final
3.84.	SP3	AE3	Summary of Adverse Events Leading to Withdrawal from Study / Permanent Discontinuation of Study Treatment by Overall Frequency: GTC3	IDSL		Y
3.85.	SP3	AE1	Summary of Special Interest Adverse Events: GTC3			Y
3.86.	SP3	AE16	Summary of Serious Adverse Events by System Organ Class and Preferred Term (Number of Participants and Occurrences): GTC3	FDAAA, EudraCT		Y

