3.145	SP1	Study specific	Number and Percentage of Subjects with PVR urine volume category (Change from Baseline): GTCs			Y
Clean Intermittent Catheterization (CIC)						
3.132.	SPDB	Study specific	Number and Percentage of Subjects with using CIC: TC1		Y	Y
3.133.	SP1	Study specific	Number and Percentage of Subjects with using CIC: GTCs			Y
3.134.	SPDB	Study specific	Number and Percentage of Subjects with using CIC by maximum PVR urine volume category		Y	Y
3.135.	SPDB	Study specific	Summary of Duration of using CIC: TC1		Y	Y
3.136.	SP1	Study specific	Summary of Duration of using CIC: GTCs			Y
3.137.	SPDB	Study specific	Time to onset of first CIC			Y
Urinary Tract Infection (UTI)						
3.138.	SPDB	Study specific	Number and Percentage of Subjects with UTI by CIC status		Y	Y
3.139.	SPDB	Study specific	Number and Percentage of Subjects with UTI by maximum PVR urine volume category		Y	Y
3.140.	SPDB	Study specific	Time to onset of UTI			Y
Urinary Retention						
3.141.	SPDB	Study specific	Summary of Duration of Urinary Retention: TC1		Y	Y
3.142.	SP1	Study specific	Summary of Duration of Urinary Retention: GTCs			Y
3.143.	SPDB	Study specific	Time to onset of Urinary Retention			Y

CONFIDENTIAL

204947

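### Table 3.133 assigns the repeat-dose CIC percentages to SP1 with no per-cycle denominator, so the GTC2 and GTC3 rates could be diluted

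*SAP*

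**What the plan says.** SAP 8 has two population rules. Adverse events (AEs) in GTC2 and GTC3 go on SP2 and SP3. Under a separate heading for everything other than AEs, GTC1, GTC2 and GTC3 all go on SP1. SAP 8.5, which covers residual volume, CIC, urinary infection and retention, repeats the second rule: "SPDB (for TC1) and SP1 (for GTC1, GTC2 and GTC3) will be used for these summaries".

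SAP 8.5.2 then asks for the CIC summary by treatment group, total and cycle: "Proportion of subjects who had used CIC at least once after the first treatment will be summarized by treatment group". It names no divisor. The matching display is Table 3.133, "Number and Percentage of Subjects with using CIC: GTCs", listed with population SP1 and produced at the final analysis only. Both the RAP of April 2018 and its amendment of July 2018 carry this rule.

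The populations are defined in SAP 4. SP1: "Comprise all subjects who receive at least one dose of GSK1358820". SP2 needs at least two doses, and its listed use is "Safety for two doses of GSK1358820 treatment". SP3 needs three. SAP 11.4.1.2 dates GTC2 from the second GSK1358820 dose and GTC3 from the third, and marks GTC3 as not applicable to subjects who started on placebo.

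Protocol 9.3.1 sets the principle for later cycles: "When analyzing the 2nd treatment cycle, the population will consist of the subjects who had a 1st and 2nd treatment". The third cycle is treated in the same way.

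**The concern.** A subject can be a CIC user in GTC2 or GTC3 only after receiving the dose that opens that cycle. If the percentage is taken over SP1, the denominator also holds people who were never at risk in the cycle, and the rate comes out too low. In the Placebo/GSK column for GTC3 it would come out as 0% for a group that cannot enter the cycle at all.

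Safety of repeated dosing is a stated objective, and CIC use is a listed safety parameter. Protocol 7.4.7 links CIC to an AE in both directions: starting CIC calls for a urinary retention AE, and that AE is recorded only where a raised residual volume requires CIC. Retention is an AE of special interest (SAP 11.6.4). It is reported on SP2 in Table 3.80 ("Summary of Special Interest Adverse Events: GTC2") and on SP3 in Table 3.85 ("Summary of Special Interest Adverse Events: GTC3"). Largely the same events could therefore appear in one report at two different rates, with CIC use seeming to fall as doses are repeated.

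**Working it through.** The plan gives no figure for this table, so there is none to reproduce. The check is which text fixes the divisor, and what follows if SP1 is used.

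**1. Is a divisor stated anywhere?**
- SAP 8.5.2 and the entry for Table 3.133: none beyond the SP1 label.
- SAP 11.12: fixes only which reasons for CIC count.
- SAP 11.5.2: asks for N, n, frequency and percentage for categorical data, without saying which is the base.
- SAP 8.3: for worst-case urinalysis, also not shown by visit, it does state the base (subjects with post-baseline data). CIC has no such sentence.
- SAP 11.13: treats CIC as log data, like AEs and concomitant medication, so no number seen at a visit can act as the divisor.

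**2. Dilution factor.** Let x be CIC users in a cycle, T the subjects treated in it and S the size of SP1. The literal percentage is x/S and the per-cycle percentage is x/T, so the first equals the second times T/S.

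**3. What the documents alone give.** Protocol 4.3 plans 120 subjects per group; take 120 dosed in each. Let P be the number of placebo-first subjects re-treated. Then S = 120 + P. Only GSK-first subjects can enter GTC3, so T is at most 120. The factor for the GTC3 total column is therefore at most 120/(120 + P):
- P = 60: 120/180 = 0.67
- P = 90: 120/210 = 0.57
- P = 120: 120/240 = 0.50

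If every subject is re-treated twice, GTC2 is not diluted (240/240 = 1.00) and GTC3 is still halved (120/240 = 0.50). The Placebo/GSK cell for GTC3 is 0/P = 0%.

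**4. Illustration on assumed uptake.** The documents give neither re-treatment shares nor a CIC rate for this trial. Assumed shares (low, middle, high):
- GSK-first: second injection 30, 50, 70%; third 10, 20, 40%.
- Placebo-first: second injection 60, 70, 90%; third 20, 40, 60%.

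As a stand-in for the risk per cycle, take the 7.1% retention rate at 100 U quoted in protocol 4.6.1.

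| Uptake | SP1 | In GTC2 | In GTC3 | GTC2 factor, shown as | GTC3 factor, shown as |
|---|---|---|---|---|---|
| Low | 120+72 = 192 | 36+24 = 60 | 12 | 0.31, 2.2% | 0.06, 0.4% |
| Middle | 120+84 = 204 | 60+48 = 108 | 24 | 0.53, 3.8% | 0.12, 0.8% |
| High | 120+108 = 228 | 84+72 = 156 | 48 | 0.68, 4.9% | 0.21, 1.5% |

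With a constant 7.1% risk, the middle case would read 7.1%, 3.8% and 0.8% over the three cycles.

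In whole subjects for that case, 7.1% of 108 is 7.7, so take 8. That is 8/108 = 7.4% on SP2 and 8/204 = 3.9% on SP1. For GTC3, 7.1% of 24 is 1.7, so take 2. That is 2/24 = 8.3% on SP3 and 2/204 = 1.0% on SP1.

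**The case against.** A reader might infer that the SAP breaks its own AE rule or contradicts SAP 4. The documents support neither. The AE rule is headed for AEs only, and CIC use follows the other rule exactly. A note under the population table in SAP 4 sends the reader to Appendix 10 for the population of each display, and Appendix 10 gives SP1 for Table 3.133. That part of the defence stands in full.

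The protocol is also less direct than it first appears. Section 9.3.1 makes the Safety Population the base for every safety analysis. It counts cycles by any study treatment, so GTC2 is the third treatment for a placebo-first subject. Section 9.4.2 plans the CIC proportion by residual-volume category, not by cycle, so SAP 2.1 had no clear departure to list. What survives is the principle: under either count, a subject not injected in a cycle does not belong in it.

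The strongest argument is that SP1 may be only the source set. SAP 8 calls for one combined GTC display, and only SP1 contains everyone in all three cycles. Table 1.18 carries the same label, yet SAP 11.6.2 limits its rows to subjects in each cycle and marks placebo-first GTC3 as not applicable. The mock shells are a separate document and may print a per-cycle n for CIC as well. This makes dilution uncertain, but it does not supply the missing divisor.

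Finally, Table 3.133 gives counts as well as percentages, Table 1.6 gives the sizes of SP1, SP2 and SP3, Tables 3.80 and 3.85 give retention on SP2 and SP3, and Listing 36 shows each CIC episode. A careful reader could recover the right rates.

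**Conclusion.** The point holds as a minor one. The population named for Table 3.133, taken at its word, gives GTC2 and GTC3 percentages over subjects who were not treated in those cycles. It departs from the cycle principle in protocol 9.3.1 and from the base used for largely the same events in the AE tables.

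The one size that needs no assumption about uptake in GTC2 or GTC3 is the ceiling of 120/(120 + P) on the GTC3 total. It rests on 120 dosed per group and on the literal reading. The GTC2 factors and the percentages in the illustration rest on assumed uptake and a borrowed rate.

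A reader might go further and conclude that the reported rates will be wrong, or that other SP1 tables share the fault. The first does not follow while the shells are unseen. Nor does the second: follow-up (Table 1.18) has no value outside a cycle, and the residual-volume category tables (3.128, 3.145) are by visit, where the number with data limits the problem. Means, durations and GTC1 are unaffected. No test, primary analysis or sample size is touched; only the descriptive account of repeat-dose safety is.

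**What to change.** For Table 3.133, and for SAP 8 and 8.5 where they govern it, do one of two things:
- keep SP1 for GTC1 and name SP2 for GTC2 and SP3 for GTC3; or
- keep the combined display, state that the denominator in each cycle is the subjects treated with GSK1358820 in that cycle, and print that n.

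Either way, show GTC3 as not applicable in the Placebo/GSK column, as SAP 11.4.1.2 and 11.6.2 already do. Tables 1.18, 3.128 and 3.145, the means and durations, and GTC1 need no change.

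The cost is one sentence or a change of label. SP2 and SP3 are already defined, and no new data are needed.
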